### 5.2.4 Rescheduling:

Nivolumab may be delayed until the next planned ipilimumab dose if the next ipilimumab dose is scheduled within the next 12 days. This will permit periodic ipilimumab dosing to be synchronized with nivolumab dosing.

Ipilimumab should be dosed at the specified interval regardless of any delays in intervening nivolumab doses. However, in order to maintain periodic synchronized dosing of ipilimumab and nivolumab, the dosing days of nivolumab and ipilimumab may be adjusted within the permitted  $\pm 5$  day window, as long as consecutive nivolumab doses are given at least 12 days apart. Ipilimumab may be delayed

beyond the 5 day window if needed to synchronize with the next nivolumab dose.

If an ipilimumab dose is delayed beyond 6 weeks from the prior ipilimumab dose, then subsequent ipilimumab doses should rescheduled to maintain the 6 week interval between consecutive ipilimumab doses.

#### 5.2.5 Continuing Nivolumab or Ipilimumab as monotherapy:

The assessment for discontinuation of nivolumab should be made separately from the assessment made for discontinuation of ipilimumab. Although there is overlap among the discontinuation criteria, if discontinuation criteria are met for nivolumab or ipilimumab (Drug 1) but not for the other (Drug 2), treatment with Drug 1 may continue if Drug 2 is discontinued.

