#### **4.6 Duration of Therapy**

Treatment will be continued for up to 2 years or discontinuation due to toxicity, withdrawal of consent, or study closure. Subjects may discontinue either drug and remain on the other agent if certain circumstances are met ([Section 5.2.7](#)).

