### 5. DOSING REDUCTIONS/DOSE DELAYS

#### 5.1 Dose Reductions

##### Recommended Dose Modifications for OPDIVO (Nivolumab)

Adverse Reaction	Severity	Dose Modification
Colitis	Grade 2 diarrhea or colitis	Withhold dose a
	Grade 3 diarrhea or colitis	Withhold dose a when administered as a single agent
	Grade 4 diarrhea or colitis	Permanently discontinue when administered with ipilimumab
Pneumonitis	Grade 2 pneumonitis	Withhold dose a
	Grade 3 or 4 pneumonitis	Permanently discontinue
Hepatitis	AST or ALT > 3 - 5 x ULN or total bilirubin > 1.5 - 3 x ULN	Withhold dose a
	AST or ALT > 5 ULN or total bilirubin > 3 x ULN	Permanently discontinue
Hypophysitis	Grade 2 or 3 hypophysitis	Withhold dose a
	Grade 4 hypophysitis	Permanently discontinue
Adrenal Insufficiency	Grade 2 adrenal insufficiency	Withhold dose a
	Grade 3 or 4 adrenal insufficiency	Permanently discontinue
Type 1 Diabetes Mellitus	Grade 3 hyperglycemia	Withhold dose a
	Grade 4 hyperglycemia	Permanently discontinue
Nephritis and Renal Dysfunction	Serum creatinine > 1.5 – 6 x ULN	Withhold dose a
	Serum creatinine > 6 x ULN	Permanently discontinue

Skin	Grade 3 rash or suspected Stevens-Johnson syndrome (SJS) or toxic epidermal necrolysis (TEN)	Withhold dose a
	Grade 4 rash or confirmed SJS or TEN	Permanently discontinue
Encephalitis	New-onset moderate or severe neurologic signs or symptoms	Withhold dose a
	Immune-mediated encephalitis	Permanently discontinue
Other	Other Grade 3 adverse reaction: First occurrence	Withhold dose a
	Recurrence of same Grade 3 adverse reactions	Permanently discontinue
	Life-threatening or Grade 4 adverse reaction	Permanently discontinue
	Grade 3 myocarditis	Permanently discontinue
	Requirement for $\geq 10$ mg per day prednisone or equivalent for $> 12$ weeks	Permanently discontinue
	Persistent Grade 2 or 3 adverse reactions lasting 12 weeks or longer	Permanently discontinue

\* Toxicity was graded per NCI CTCAE v4.

a Resume treatment when adverse reaction improves to Grade 0 or 1.

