#### **Recommended Treatment Modifications for Immune-Mediated Adverse Reactions of YERVOY (Ipilimumab)**

Target/Organ System	Adverse Reaction	Treatment Modification
Endocrine	Symptomatic endocrinopathy	Withhold dose  Resume in patients with complete or partial resolution of adverse reactions (Grade 0 to 1) and who are receiving $< 7.5$ mg prednisone or equivalent per day.
	
 
• Symptomatic reactions lasting 6 weeks or longer
 
• Inability to reduce corticosteroid dose to <math>< 7.5</math> mg prednisone or equivalent per day
 
	Permanently discontinue
Ophthalmologic	Grade 2 through 4 reactions 
 
• not improving to Grade 1 within 2 weeks while receiving topical therapy or
 
• requiring systemic treatment
 
	Permanently discontinue
All Other	Grade 2	Withhold dose  Resume in patients with complete or partial resolution of adverse reactions (Grade 0 to 1) and who are receiving $< 7.5$ mg prednisone or equivalent per day.

	
 
• Grade 2 reactions lasting 6 weeks or longer
 
• Inability to reduce corticosteroid dose to 7.5 mg prednisone or equivalent per day
 
• Grade 3 or 4
 
	Permanently discontinue
--	---	-------------------------

The NCI Common Terminology Criteria for Adverse Events (CTCAE) Version 4.0 will be used to grade adverse events.

Patients enrolled in this study will be evaluated clinically and with standard laboratory tests before and at regular intervals during their participation in this study.

Patients will be evaluated for adverse events (all grades), serious adverse events, and adverse events requiring study drug interruption or discontinuation at each study visit for the duration of their participation in the study.

Due to the prolonged half-life associated with monoclonal antibodies, no dose reductions of either study agent are planned.

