### 5.2.1 Criteria for Permanent Discontinuation of Nivolumab and Ipilimumab

- In addition to the treatment discontinuation parameters in 6.1, any treatment-related event that leads to delay in dosing lasting >12 weeks from ipilimumab dosing OR > 6 weeks from nivolumab dosing requires discontinuation, with the following exceptions:
  - Dosing delays within those time frames to allow for prolonged steroid tapers to manage drug-related adverse events are allowed.
  - Dosing delays lasting >12 weeks of ipilimumab or > 6 weeks of nivolumab from the previous dose that occur for non-drug-related reasons may be allowed.
- Any adverse event, laboratory abnormality, or intercurrent illness which, in the judgment of the Investigator, presents a substantial clinical risk to the participant with continued dosing.

Periodic study visits to assess safety and laboratory studies should also continue every 6 weeks or more frequently if clinically indicated during such dosing delays.

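### Section 5.2.5 transposes its drug labels: read literally, the drug that met stopping criteria may continue if the other is stopped, which contradicts the Section 5.1 tables

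*Combined protocol and SAP*

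**What the plan says.** Section 5.2.5 first asks for the two drugs to be assessed for discontinuation separately. It then sets up its terms: "if discontinuation criteria are met for nivolumab or ipilimumab (Drug 1"). That makes Drug 1 the drug with a reason to stop, and Drug 2 is the drug without one. For this situation the sentence concludes: "but not for the other (Drug 2), treatment with Drug 1 may continue if Drug 2 is discontinued".

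Section 4.6 gives the general permission: "Subjects may discontinue either drug and remain on the other agent if certain circumstances are met". For those circumstances it sends the reader to Section 5.2.7, but Section 5.2 ends at 5.2.5.

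Section 5.1 holds a separate table for each drug, and each table marks certain events for permanent discontinuation of that drug. The ipilimumab table is headed "Recommended Treatment Modifications for Immune-Mediated Adverse Reactions of YERVOY (Ipilimumab").

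Section 5.2.1 adds time limits: "In addition to the treatment discontinuation parameters in 6.1, any treatment-related event that leads to delay in dosing" beyond 12 weeks for ipilimumab or 6 weeks for nivolumab requires discontinuation, with stated exceptions. The parameters it cites as 6.1 are evidently the Section 5.1 tables, because Section 6.1 contains adverse-event definitions. Section 5.2.3 separately requires ipilimumab to stop after a treatment-related gap of more than 12 weeks.

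**The concern.** This clause is the only place where the protocol sets out, in terms of which drug met criteria, when a subject may go on with a single agent. It applies after toxicity serious enough to stop one of two immune checkpoint inhibitors. Taken at its word, it lets the subject continue the drug that the tables say to stop for good, on condition that the drug with no reason to stop is withdrawn. It is also silent on the option that was presumably meant, which is to stay on the unaffected drug alone. A site that does the right thing would have to rely on Section 4.6 and the tables, and read Section 5.2.5 against its own words.

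**Working it through.** No arithmetic applies. The check is to put the section's own definitions into its last clause and compare the result with the other rules.

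**Step 1: substitute.** Drug 1 is the drug for which criteria are met. Drug 2 is the drug for which they are not. The clause then reads: the drug that met criteria may continue if the drug that did not is stopped. The labels as defined allow no other reading.

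**Step 2: find a case where the two tables in Section 5.1 diverge.** The clause operates only if one drug must stop and the other need not. An immune-mediated Grade 3 rash is such a case:

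| Drug | Where in Section 5.1 | Instruction | Label under 5.2.5 |
|---|---|---|---|
| Ipilimumab | All Other row, Grade 3 or 4 (the table has no skin row) | Stop permanently | Drug 1 |
| Nivolumab | Skin row: "Grade 3 rash or suspected Stevens-Johnson syndrome (SJS) or toxic epidermal necrolysis (TEN") | Withhold, resume at Grade 0 or 1 | Drug 2 |

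**Step 3: compare the outcomes.**
- Section 5.1: ipilimumab ends, and nivolumab may resume once the rash has improved.
- Section 5.2.5 as worded: ipilimumab may continue if nivolumab ends. This is the opposite of the tables.
- Section 5.2.5 with the labels swapped: nivolumab may continue once ipilimumab is stopped. This agrees with the tables and with the evident sense of Section 4.6.

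**Step 4: check the time-based rules.** Suppose ipilimumab has passed the 12-week treatment-related limit and nivolumab has met no criterion of its own. Ipilimumab is again Drug 1. Sections 5.2.1 and 5.2.3 require it to stop, while Section 5.2.5 as worded would let it continue.

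**Step 5: ask when the clause takes effect.** Section 5.2 delays both drugs for a drug-related toxicity that meets the delay criteria, until retreatment criteria are met. The clause therefore matters at resumption, when someone decides which drug to restart.

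**Step 6: size.** The documents give no frequency for the events on which the tables diverge. The nearest figures are the 37% and 33% rates of Grade 3-4 treatment-related events in the two lung cancer cohorts described in Section 2.3.1. Those rates pool all such events in another disease and do not show how often one drug stops and the other does not. No count of affected subjects follows from them.

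**The case against.** The best answer is that a competent investigator would see the slip. The literal rule tells the site to withdraw the drug with no reason to stop and keep the one ordered stopped, which is implausible on its face. The first sentence of Section 5.2.5 calls for separate assessment, the Section 5.1 entries are explicit, and Section 4.6 allows a subject to stay on the other agent. Section 5.2.1 also requires stopping for any event that the investigator judges a substantial clinical risk. All of this stands, and it limits the severity. It does not make the clause right. A rule on permanent discontinuation should not need other sections to reverse it.

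A reader might infer more than the documents support:

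- *That Section 4.6 says the exact opposite.* It does not say which drug met criteria, so the conflict is with its evident intent. The direct contradiction is with Sections 5.1, 5.2.1 and 5.2.3.
- *That the intended option is forbidden.* Section 5.2.5 is silent on it, and Section 4.6 permits it.
- *That every first Grade 3 reaction sets the tables against each other.* The nivolumab row "Other Grade 3 adverse reaction: First occurrence" covers any such reaction, but the ipilimumab table is limited to immune-mediated ones.
- *That a Grade 2 reaction lasting 6 to under 12 weeks is a clean example.* The two tables do differ there. But Section 5.2 delays both drugs, and the 6-week nivolumab limit in Section 5.2.1 would normally stop nivolumab too.
- *That severe endocrine events give equally firm examples in the other direction.* Treating them as such leans on the endocrine grouping in Section 6.6.1, which serves the safety analysis. Sections 5.2.2 and 5.2.3 also have their own resumption rules for endocrinopathies controlled on hormone replacement.

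For these reasons no tally of diverging situations is offered. The rash example is enough to show the error.

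**Conclusion.** The transposition is certain from the text of Section 5.2.5 alone. As worded, the clause conflicts directly with the permanent-discontinuation entries in Section 5.1 and with the stopping rules in Sections 5.2.1 and 5.2.3. It should be corrected because it is an operative safety instruction, although the correction is one of wording. The practical risk is reduced by the hold on both drugs and by the recoverable intent, and its frequency cannot be estimated. A reader might infer that the efficacy result is at stake. The documents do not support that: the definition of ORR, the 20 and 56 patient stages and the rejection rule do not depend on this clause. The worked example assumes that the rash is immune-mediated and, having no row of its own, falls under All Other in the ipilimumab table.

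**What to change.** Swap the labels in the last clause of Section 5.2.5, so that it says Drug 2 may continue if Drug 1 is discontinued. In Section 4.6, replace the reference to Section 5.2.7 with Section 5.2.5. While the text is open, the references to 6.1 in Sections 5.2 and 5.2.1 could be corrected to 5.1, which is tidying and not essential. The cost is a wording amendment and a notice to sites, with no change to the sample size, the stopping boundary or any analysis.

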### 5.3 Treatment Beyond Progression

Accumulating evidence indicates a minority of subjects treated with immunotherapy may derive clinical benefit despite initial evidence of PD (26).

Subjects will be permitted to continue on nivolumab + ipilimumab for treatment beyond initial RECIST 1.1 defined PD as long as they meet the following criteria:

- Investigator-assessed clinical benefit and no rapid disease progression
- Subject is tolerating study treatment
- Stable performance status
- Treatment beyond progression will not delay an imminent intervention to prevent serious complications of disease progression (e.g., CNS metastases)

The decision to continue treatment beyond initial investigator-assessed progression should be discussed with the IND Sponsor and documented in the study records. A follow-up scan should be performed within six (6) weeks +/- 5 days of original PD to determine whether there has been a decrease in the tumor size, or continued progression of disease. Subsequent scans should be performed every twelve (12) weeks until further progression is determined.

If the investigator feels that the subject continues to achieve clinical benefit by continuing treatment, the subject should remain on the trial and continue to receive monitoring according to the Time and Events Schedule on [study calendar \(Section 9\)](#).

For the subjects who continue study therapy beyond progression, further progression is defined as an additional 10% increase in tumor burden from time of initial PD. This includes an increase in the sum of diameters of all target lesions and/ or the diameters of new measurable lesions compared to the time of initial PD. Nivolumab and ipilimumab treatment should be discontinued permanently upon documentation of further progression.

New lesions are considered measureable at the time of initial progression if the longest diameter is at least 10 mm (except for pathological lymph nodes which must have a short axis of at least 15 mm). Any new lesion considered non-measureable at the time of initial progression may become measureable and therefore included in the tumor burden if the longest diameter increases to at least 10 mm (except for pathological lymph nodes which

must have a short axis of at least 15 mm). In situations where the relative increase in total tumor burden by 10% is solely due to inclusion of new lesions which become measurable, these new lesions must demonstrate an absolute increase of at least 5 mm.

#### **5.4 Management Algorithms for Immuno-Oncology Agents**

Immuno-oncology (I-O) agents are associated with AEs that can differ in severity and duration than AEs caused by other therapeutic classes. Nivolumab and ipilimumab are considered immuno-oncology agents in this protocol. Early recognition and management of AEs associated with immuno-oncology agents may mitigate severe toxicity.

Management Algorithms have been developed to assist investigators in assessing and managing the following groups of AEs:

- Gastrointestinal
- Renal
- Pulmonary
- Hepatic
- Endocrinopathy
- Skin
- Neurological

The above algorithms are found in both the Nivolumab and Ipilimumab Investigator Brochures, as well as in [Appendix 2](#).

#### **5.5 Management of Nivolumab or Ipilimumab Infusion Reactions**

Since nivolumab and ipilimumab contain only human immunoglobulin protein sequences, they are unlikely to be immunogenic and induce infusion or hypersensitivity reactions. However, if such a reaction were to occur, it might manifest with fever, chills, rigors, headache, rash, pruritus, arthralgias, hypo- or hypertension, bronchospasm, or other symptoms. All Grade 3 or 4 infusion reactions should be reported within 24 hours to the IND Sponsor and reported as an SAE if criteria are met. Infusion reactions should be graded according to NCI CTCAE (Version 4.0) guidelines.

Treatment recommendations are provided below and may be modified based on local treatment standards and guidelines, as appropriate:

##### **5.5.1 For Grade 1 symptoms: (mild reaction; infusion interruption not indicated; intervention not indicated)**

Remain at bedside and monitor subject until recovery from symptoms. The following prophylactic premedications are recommended for future infusions: diphenhydramine 50 mg (or equivalent) and/or acetaminophen 325 to 1000 mg at least 30 minutes before additional nivolumab or ipilimumab administrations.

##### **5.5.2 For Grade 2 symptoms: (moderate reaction requires therapy or infusion interruption but responds promptly to symptomatic treatment [e.g., antihistamines, non-steroidal anti-inflammatory drugs, narcotics, corticosteroids, bronchodilators, IV fluids]; prophylactic medications indicated for $\geq$ 24 hours)**

Stop the nivolumab or ipilimumab infusion, begin an IV infusion of normal saline,

and treat the subject with diphenhydramine 50 mg IV (or equivalent) and/or acetaminophen/paracetamol 325 to 1000 mg; remain at bedside and monitor subject until resolution of symptoms. Corticosteroid and/or bronchodilator therapy may also be administered as appropriate. If the infusion is interrupted, then restart the infusion at 50% of the original infusion rate when symptoms resolve; if no further complications ensue after 30 minutes, the rate may be increased to 100% of the original infusion rate. Monitor subject closely. If symptoms recur, then no further nivolumab or ipilimumab will be administered at that visit. Administer diphenhydramine 50 mg IV, and remain at bedside and monitor the subject until resolution of symptoms. The amount of study drug infused must be recorded on the electronic case report form (eCRF).

For future infusions, the following prophylactic premedications are recommended: diphenhydramine 50 mg (or equivalent) and/or acetaminophen 325 to 1000 mg should be administered at least 30 minutes before nivolumab or ipilimumab infusions. If necessary, corticosteroids (up to 25 mg of SoluCortef or equivalent) may be used.

5.5.3 For Grade 3 or 4 symptoms: (severe reaction, Grade 3: prolonged [i.e., not rapidly responsive to symptomatic medication and/or brief interruption of infusion]; recurrence of symptoms following initial improvement; hospitalization indicated for other clinical sequelae [e.g., renal impairment, pulmonary infiltrates]. Grade 4: Life threatening; pressor or ventilatory support indicated)

Immediately discontinue infusion of nivolumab or ipilimumab. Begin an IV infusion of normal saline and treat the subject as follows: Recommend bronchodilators, epinephrine 0.2 to 1 mg of a 1:1000 solution for subcutaneous administration or 0.1 to 0.25 mg of a 1:10,000 solution injected slowly for IV administration, and/or diphenhydramine 50 mg IV with methylprednisolone 100 mg IV (or equivalent), as needed. Subject should be monitored until the investigator is comfortable that the symptoms will not recur. Nivolumab or ipilimumab will be permanently discontinued. Investigators should follow their institutional guidelines for the treatment of anaphylaxis. Remain at bedside and monitor subject until recovery of the symptoms.

In case of late-occurring hypersensitivity symptoms (e.g., appearance of a localized or generalized pruritus within 1 week after treatment), symptomatic treatment may be given (e.g., oral antihistamine or corticosteroids).

## 6. ADVERSE EVENTS: LIST AND REPORTING REQUIREMENTS

This study will use the descriptions and grading scales found in the revised National Cancer Institute Common Terminology Criteria for Adverse Events (CTCAE) Version 4.0 for adverse event reporting that can be found at [http://ctep.cancer.gov/protocolDevelopment/electronic\\_applications/ctc.htm](http://ctep.cancer.gov/protocolDevelopment/electronic_applications/ctc.htm).

Information about all AEs, whether volunteered by the subject, discovered by investigator questioning, or detected through physical examination, laboratory test or other means, will be collected, recorded, and followed as appropriate.

All AEs and SAEs experienced by subjects will be collected and reported from the first dose of nivolumab, throughout the study, and will only be followed for 4 weeks unless related to the investigational agent. All SAEs will be collected for 100 days after the last dose of nivolumab. Subjects who have an ongoing AE related to the study procedures and/or medication(s) may continue to be periodically contacted by a member of the study staff until the event is resolved or determined to be irreversible by the investigator.

**Laboratory abnormalities:** Laboratory abnormalities present at the screening visit will be recorded as pre-treatment signs and symptoms. After study treatment administration, all grade 3 and 4 clinical laboratory results that represent an increase in severity from baseline will be reported as adverse events. A grade 1 or 2 clinical laboratory abnormality should be

